Lapatinib Safety Safety results from Phase I monotherapy studies in cancer patients indicate that lapatinib administered on a QD schedule was generally well tolerated at doses of lapatinib ranging from 175 mg to 1800 mg QD. Doses of 500 and 750 BID were better tolerated than 900 mg BID.⁶⁵ The majority of AEs were Grade 1 or 2 gastrointestinal and/or skin toxicities. The incidence of diarrhea increased with increasing dose, whereas the incidence of rash was not related to dose. The Phase II/Phase III program had enrolled a total of 1581 subjects. Of these, 1001 subjects were enrolled in Phase II monotherapy studies. Data suggest that lapatinib administered as monotherapy at doses of 1250 mg QD, 1500 mg QD, and 500 mg BID is generally well tolerated. For the completed and ongoing Phase II and Phase III studies, the preliminary safety data was similar to what has been observed in the Phase I monotherapy studies and combination studies. The most common AEs considered related by the investigator were gastrointestinal (diarrhea, nausea, vomiting), rash, fatigue, and anorexia. The majority of all AEs were Grade 1 and Grade 2.

SAE data from ongoing lapatinib studies (all phases) are from 2312 subjects treated with lapatinib.⁶⁵ For the ongoing studies, a total of 831 SAEs were reported from 405 individual subjects. The most frequently reported SAE was diarrhea, with a total of 47 reports, 37 of which were assessed as related to investigational product. Dyspnea, vomiting, dehydration, and nausea were also among the most frequently reported SAEs regardless of relatedness. Overall, 24.6% of the SAEs reported were assessed as related to investigational product by the investigator. The most frequently reported drug-related events were: diarrhea, neutropenia, vomiting, nausea, dehydration, and decreased ejection fraction. Diarrhea which may lead to dehydration, nausea, and vomiting are all included in the development core safety information for lapatinib. Interstitial pneumonitis and two cases of interstitial pneumonia have been reported in the lapatinib program. Subjects on the lapatinib program have experienced a decrease in LVEF, giving an approximate incidence for this event of 1.4%.

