3.0 STUDY DESIGN (Table 1 and Figure 7)

The study is an open-label, single arm, single institution, pilot clinical trial of Veliparib (a PARP inhibitor) in combination with Lapatinib (an EGFR inhibitor) in patients with pathologically confirmed TNBC (ER negative, PR negative, HER-2-Neu negative by IHC [0, 1] or FISH) who have not received prior therapy in the metastatic setting (but failed anthracyclines and taxanes in the

neoadjuvant or adjuvant setting) or who have failed prior chemotherapy in the metastatic setting (including anthracyclines and taxanes and no more than two prior regimens for metastatic disease as long as patients have adequate performance status – see Appendix B). The data obtained in this pilot study will be used to design a phase II clinical trial that will be conducted by the Translation Breast Cancer Research Consortium.

As described in **Figure 7**, patients will receive Lapatinib (1250 mg PO daily continuously) in combination with Veliparib (200 mg PO every 12 hours continuously). A cycle of therapy is defined as 28 days of PO therapy. Lapatinib will start Day 1 cycle 1 and Veliparib will start on Day 2 Cycle 1 (for better understanding of the PK of the drugs as well as to induce a DSB repair defect first with Lapatinib). Dose reductions of Lapatinib and Veliparib will be allowed. Patients developing grade 1 and 2 toxicities will be permitted to take a drug holiday of up to 14 days; after the drug holiday, if the adverse event has resolved to the satisfaction of the investigator, the study drugs may be resumed at the same level. In the event of recurrent toxicity, there will be two dose reductions permitted (dose reduction minus one will be Lapatinib 1000 mg PO daily continuously and Veliparib 150 mg PO every 12 hours continuously); dose reduction minus two will be Lapatinib 750 mg PO daily and Veliparib 100 mg PO every 12 hours continuously. If the adverse event recurs after dose reduction two, the patient will be taken off the study. Patients developing grade 3 and 4 toxicities will be interrupted for up to 14 days; after the drug holiday, if the adverse event has resolved to the satisfaction of the investigator, the study drugs may be resumed at a reduced dose (Lapatinib 1000 mg PO daily continuously and Veliparib 150 mg PO every 12 hours continuously). If the adverse event recurs, the patient will be taken off the study.

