Hepatotoxicity (ALT or AST >3 times the upper limit of normal and total bilirubin >2 times the upper limit of normal) has been observed in clinical trials (<1% of patients) and post-marketing experience. The hepatotoxicity may be severe and deaths have been reported. Causality of the deaths is uncertain. The hepatotoxicity may occur days to several months after initiation of treatment. Liver function tests (transaminases, bilirubin, and alkaline phosphatase) should be monitored before initiation of treatment, every 4 to 6 weeks during treatment, and as clinically indicated. If changes in liver function are severe, therapy with lapatinib should be discontinued and patients should not be retreated.

No pulmonary toxicity has been noted with lapatinib. However, interstitial lung disease (ILD) has been described in mainly lung cancer patients receiving tyrosine kinase inhibitors against HER1, like gefitinib. Interstitial lung disease, which may be acute in onset, has been observed uncommonly in patients treated with gefitinib. These patients usually present with a fairly acute onset of dyspnea,

sometimes associated with cough or low-grade fever. This may become quite severe within a short period of time and usually results in hospitalization. Radiological investigations, often including CT scan, frequently show pulmonary infiltrates or interstitial shadowing with ground-glass appearance. There is often respiratory distress with arterial oxygen desaturation. Cultures are frequently negative for bacterial growth. If patients present with an acute worsening of respiratory symptoms such as dyspnea, cough, and fever, lapatinib will be interrupted and the patient promptly investigated for ILD. If ILD is confirmed, lapatinib will be discontinued and the patient treated appropriately.

QT prolongation was observed in an uncontrolled, open-label dose escalation study of lapatinib in advanced cancer patients. Lapatinib should be administered with caution to patients who have or may develop prolongation of QTc. These conditions include patients with hypokalemia or hypomagnesemia, with congenital long QT syndrome, patients taking anti-arrhythmic medicines or other medicinal products that lead to QT prolongation, and cumulative high-dose anthracycline therapy. Hypocalcemia, hypokalemia, and hypomagnesemia should be corrected prior to lapatinib administration.

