5.2.3 Lapatinib Dosing

The daily dose of Lapatinib will be 1250 mg PO every 24 hours continuously for 28 days (a cycle). Patients developing grade 1 and 2 toxicities will be permitted to take a drug holiday of up to 14 days; after the drug holiday, if the adverse event has resolved to the satisfaction of the investigator, the study drug may be resumed at the same level. In the event of recurrent toxicity, there will be two dose reductions permitted (Lapatinib 1000 mg PO every 24 hours continuously and Lapatinib 750 mg PO daily). If the adverse event recurs, the patient will be taken off the study. Patients developing grade 3 and 4 toxicities will be permitted to take a drug holiday of up to 14 days; after the drug holiday, if the adverse event has resolved to the satisfaction of the investigator, the study drugs may be resumed at a reduced dose (Lapatinib 1000 mg PO every 12 hours continuously). If the adverse event recurs, the patient will be taken off the study. Lapatinib will start on day 1.

Patients should be carefully instructed by study personnel on how to take lapatinib. Patients will be instructed to take lapatinib, 1250 mg (5 tablets) PO on a daily basis, at approximately the same time each day. Lapatinib must be taken on an empty stomach—either 1 hour (or more) before a meal or 1 hour (or more) after a meal. Patients may not use anything but water to help them swallow their lapatinib. Medications that modify gastric pH, while not prohibited, are restricted and further described in the table of prohibited medications. Histamine H₂ antagonists and proton pump inhibitors are allowed. NOTE: Lapatinib is not to be taken with grapefruit or grapefruit juice. Grapefruit and grapefruit juice should not be taken at any time during the study. If the patient vomits after their lapatinib dose, the patient should be instructed not to retake the dose. Patients should take the next regularly scheduled dose of lapatinib. If vomiting persists, the patient should contact their study doctor.

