Patients who have a $\geq 20\%$ decrease in left ventricular cardiac ejection fraction relative to baseline, and the ejection fraction is below the institution's lower limit of normal, should have a repeat evaluation of ejection fraction 1-2 weeks later while still receiving investigational product. If the repeat ejection fraction evaluation confirms a $\geq 20\%$ decrease in left ventricular cardiac ejection fraction, and the ejection fraction is below the institution's lower limit of normal, then lapatinib should be temporarily discontinued. If the left ventricular ejection fraction recovers during the next 3 weeks, the patient may be restarted on investigational product at a reduced dose. For such patients, monitoring of left ventricular ejection fraction will then be performed 2 weeks and 4 weeks after rechallenge, and then every 4 weeks thereafter. If repeat ejection fraction evaluation still shows a decrease $\geq 20\%$ in left ventricular ejection fraction relative to baseline, and the value is below the institution's lower limit of normal, then the subject should be withdrawn from investigational product. Patients with an NCI CTCAE grade 3 or 4 LVEF relative decrease must be withdrawn from study medications. Patients will be monitored closely for pulmonary toxicity. Patients with an NCI CTCAE Grade 3 or 4 interstitial pneumonitis must be withdrawn from study medications.

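### The general dose-modification rules contradict the lung-specific rules for confirmed ILD or interstitial pneumonitis, with no stated precedence, and sections 5.2.2 and 2.6 disagree on whether lung events have been seen with lapatinib

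*Combined protocol and SAP*

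**What the plan says.** **Lung-specific rules.** Section 5.2.2 has two steps. On acute worsening of respiratory symptoms, "lapatinib will be interrupted and the patient promptly investigated for ILD". Then: "If ILD is confirmed, lapatinib will be discontinued and the patient treated appropriately". Neither step mentions a grade, and nothing describes a restart after confirmation. Section 6.2.3 says: "Patients with an NCI CTCAE Grade 3 or 4 interstitial pneumonitis must be withdrawn from study medications". Footnote 10 of the section 6.6 table repeats that sentence. Neither place says what happens at grade 1 or 2.

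**General toxicity rules.** Section 3.0 says: "Patients developing grade 1 and 2 toxicities will be permitted to take a drug holiday of up to 14 days". If the event has then resolved to the investigator's satisfaction, "the study drugs may be resumed at the same level". After a grade 3-4 toxicity, 3.0 allows an interruption of up to 14 days followed by a restart at a lower dose. Sections 5.1.5 (veliparib) and 5.2.3 (lapatinib) repeat both rules; the lapatinib text for grades 1-2 reads "the study drug may be resumed at the same level". The Cohort -1 paragraph at the end of 3.0 repeats the grade 1-2 rule. None of these texts excepts ILD or pneumonitis.

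**Background on lung events.** Section 5.2.2: "No pulmonary toxicity has been noted with lapatinib". Section 2.6: "Interstitial pneumonitis and two cases of interstitial pneumonia have been reported in the lapatinib program".

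**The concern.** An investigator with a patient who has confirmed ILD needs one instruction. Here the answer depends on which section is opened. A low-grade event that settles within the 14-day hold falls under a lapatinib stop in 5.2.2 and under a permitted same-level restart in 3.0 and 5.2.3. A high-grade event that settles falls under mandatory withdrawal in 6.2.3 and 6.6 and under a permitted reduced-dose restart in 3.0, 5.1.5 and 5.2.3.

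The stake is patient safety. Section 5.2.2, describing the experience with gefitinib, says the condition can worsen quickly and usually leads to hospital admission. Consistent conduct is also at stake: safety and tolerance are the primary objective, and two patients with the same event could be handled differently, each in line with some part of the protocol.

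The two statements on lung events compound this. The drug-information section is where an investigator would look for known lapatinib risks, and it does not match the safety summary in the background.

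**Working it through.** No arithmetic applies; the check is a comparison of texts. Take a confirmed ILD or interstitial pneumonitis that resolves within a 14-day hold, and read off each instruction.

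| Text | Grade 1-2 | Grade 3-4 |
|---|---|---|
| 5.2.2 (lapatinib) | Discontinue on confirmation | Discontinue on confirmation |
| 6.2.3 and 6.6 footnote 10 (study medications) | Silent | Withdrawal mandatory |
| 3.0, 5.1.5, 5.2.3 (general rule) | May restart at same level | May restart at reduced dose |
| 3.0, Cohort -1 paragraph | May restart at same level | Not spelled out; the cohort is said to follow the rules of the starting cohort |

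1. **Grade 1-2.** Two texts give an outcome, and they conflict for lapatinib: 5.2.2 stops it, and 3.0 with 5.2.3 permits it again at the same level. Sections 6.2.3 and 6.6 give no outcome in this column.

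2. **Grade 3-4.** Sections 5.2.2, 6.2.3 and 6.6 all stop lapatinib. The general rules in 3.0, 5.1.5 and 5.2.3 permit a restart at a reduced dose. The conflict is between the general rule and every lung-specific rule.

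3. **5.2.2 against 6.2.3 and 6.6.** These can be obeyed together: stop lapatinib on confirmation, and take the patient off study medications at grade 3-4. They differ in trigger (confirmation or grade), in term (ILD or interstitial pneumonitis) and in scope (lapatinib or study medications). The protocol does not define the two terms as distinct conditions. Section 4.3 partly bridges the scope, because it bars single-agent continuation after unacceptable toxicity to one drug.

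4. **Precedence.** No section says that an organ-specific rule overrides the general one.

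5. **Meaning of the stop in 5.2.2.** The text moves from interruption during work-up to discontinuation on confirmation. Section 6.2.3 adds the word *temporarily* when it means a temporary stop for ejection fraction. On the other side, the liver paragraph of 5.2.2 expressly bars re-treatment, and the ILD sentence does not. The text therefore gives no route back but does not expressly forbid one.

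6. **Link to the primary endpoint.** The counted toxicities in 3.0, 7.1 and 7.6 include non-hematologic events at grade 3 or 4 (with listed exceptions), and failure to recover after a delay of more than 14 days. A grade 1-2 event that resolves within the hold meets neither. A drug-related grade 3-4 pneumonitis is counted whether or not treatment restarts. The conflicts in the table therefore do not by themselves change the count for these events.

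7. **Lung events.** Section 5.2.2 says none has been noted with lapatinib; 2.6 reports some in the lapatinib program. As background for an investigator, the two statements do not fit together.

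**The case against.** The strongest reply is that a specific rule ordinarily governs a general one. The protocol keeps organ-specific rules for ejection fraction, liver and diarrhea alongside the general rule. Section 3.0 is also permissive: it allows a restart, leaves resolution to the investigator and compels nothing. On that reading the lung-specific texts prevail, and the defect is a missing precedence sentence. This has force, and it may well be what was intended. It is nowhere stated, however, and it would still leave grade 1-2 events resting on 5.2.2 alone, with different terms and scope in 6.2.3 and 6.6.

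On the background statements, it can be said that 2.6 reports cases in the program without assigning cause, while 5.2.2 speaks of toxicity. That is fair: the documents do not show which sentence is accurate, so 5.2.2 cannot be called false from them. The mismatch stands.

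A reader might also infer that the 5.2.2 sentence biases causality judgments, so that a pneumonitis is put down to the cancer. That is speculative. The same paragraph goes on to warn of ILD with HER1 inhibitors and requires prompt investigation. Section 6.2.3 requires close pulmonary monitoring, section 9.1.2 makes grade 3 pneumonitis a reportable serious event, and the causality definitions in section 9 turn on timing and alternative explanations.

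**Conclusion.** The inconsistency is real and should be corrected. For confirmed ILD or interstitial pneumonitis, the general rules contradict 5.2.2 at grades 1-2 and contradict the lung-specific withdrawal rule at grades 3-4, with no stated precedence. Sections 5.2.2 and 2.6 also disagree on lung events.

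Three stronger readings are not supported:

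- **A permanent stop against withdrawal only at grade 3-4.** Neither *permanent* nor *only* is in the text. Section 5.2.2 is silent on re-treatment, and 6.2.3 and 6.6 set a mandatory minimum.
- **Three different outcomes for one grade 1-2 event.** There are two, because 6.2.3 and 6.6 give none at that grade.
- **A shift in the primary toxicity rate.** One event in 20 patients is 1/20 = 5 percentage points, but that holds for any event. A resolved grade 1-2 event is not counted, so the figure does not follow from this conflict.

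The consequence is a risk to patient safety and to consistent conduct, not a quantified statistical effect. The conclusion assumes that ILD and interstitial pneumonitis are meant as the same kind of event, since the protocol does not separate them. No view is taken on which rule is clinically right.

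**What to change.** The clinical team should reconcile 3.0 (including the Cohort -1 paragraph), 5.1.5, 5.2.2, 5.2.3, 6.2.3 and footnote 10 of 6.6 into one consistent ILD/pneumonitis rule. That rule should:

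- use one term, or define the two terms;
- cover grades 1-2 as well as 3-4;
- name the drugs it applies to;
- say whether treatment may restart;
- say whether it overrides the general dose-modification rule.

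The statements on lung events in 5.2.2 and 2.6 should be checked against the current investigator's brochure and made to agree.

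The cost is amendment wording in seven sections (the six above plus 2.6). No visit, test or analysis is added, and the sample size and stopping boundary are unchanged.

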5.2.3 Lapatinib Dosing

The daily dose of Lapatinib will be 1250 mg PO every 24 hours continuously for 28 days (a cycle). Patients developing grade 1 and 2 toxicities will be permitted to take a drug holiday of up to 14 days; after the drug holiday, if the adverse event has resolved to the satisfaction of the investigator, the study drug may be resumed at the same level. In the event of recurrent toxicity, there will be two dose reductions permitted (Lapatinib 1000 mg PO every 24 hours continuously and Lapatinib 750 mg PO daily). If the adverse event recurs, the patient will be taken off the study. Patients developing grade 3 and 4 toxicities will be permitted to take a drug holiday of up to 14 days; after the drug holiday, if the adverse event has resolved to the satisfaction of the investigator, the study drugs may be resumed at a reduced dose (Lapatinib 1000 mg PO every 12 hours continuously). If the adverse event recurs, the patient will be taken off the study. Lapatinib will start on day 1.

Patients should be carefully instructed by study personnel on how to take lapatinib. Patients will be instructed to take lapatinib, 1250 mg (5 tablets) PO on a daily basis, at approximately the same time each day. Lapatinib must be taken on an empty stomach—either 1 hour (or more) before a meal or 1 hour (or more) after a meal. Patients may not use anything but water to help them swallow their lapatinib. Medications that modify gastric pH, while not prohibited, are restricted and further described in the table of prohibited medications. Histamine H₂ antagonists and proton pump inhibitors are allowed. NOTE: Lapatinib is not to be taken with grapefruit or grapefruit juice. Grapefruit and grapefruit juice should not be taken at any time during the study. If the patient vomits after their lapatinib dose, the patient should be instructed not to retake the dose. Patients should take the next regularly scheduled dose of lapatinib. If vomiting persists, the patient should contact their study doctor.

In vitro data suggest the possibility of drug-drug interactions with lapatinib involving metabolic enzymes and transporter proteins. Because lapatinib is predominantly eliminated by metabolism through CYP3A4/5, drugs that inhibit or induce these enzymes may alter systemic exposure. Ketoconazole, a CYP3A4 inhibitor, has been shown to elevate lapatinib plasma concentrations 3.5-fold. Carbamazepine, a CYP3A4 inducer, has been shown to reduce lapatinib plasma concentrations by 72%. Therefore, use of lapatinib with drugs that alter CYP3A4/5 activity should be undertaken with caution. Lapatinib has been shown to modestly inhibit CYP3A4 and Pgp, and potently inhibit BCRP at in vitro concentrations near the high end of those expected clinically. In the absence of clinical data, use of lapatinib with drugs that are substrates for CYP3A4, Pgp, and BCRP should

proceed with caution. For a comprehensive list of prohibited medications, please refer to Appendix H.

In August 2011, the lapatinib prescribing information was revised to include information regarding potential interactions with midazolam and digoxin. Following co-administration of lapatinib and midazolam, 24-hour systemic exposure of orally administered midazolam increased by 45%, while 24-hour systemic exposure of intravenously administered midazolam increased by 22%. The use of midazolam for a procedure (e.g. port placement) is permitted; however, investigators and patients should be aware of the potential interaction. Following co-administration of lapatinib and digoxin, systemic concentration of oral digoxin increased approximately 2.8-fold. Concomitant use of digoxin is not prohibited; however, every effort should be made to switch the patient to a suitable alternative. In the event that an alternative to digoxin is not available, serum digoxin concentrations should be monitored prior to the initiation of lapatinib therapy, and throughout co-administration. If the digoxin serum concentration is greater than 1.2 ng/mL, the digoxin dose should be reduced by half.

